APPENDIX

A1. Diagnosis of RDS:

Respiratory distress appearing within the first 24 h of life, with complete, sustained, and prompt response to surfactant or lung recruitment or both; additional non-mandatory criteria are

lung imaging (chest X-rays or ultrasound, according to local policies) supporting the diagnosis or lamellar body counts $\leq 30\,000/\text{mm}^3$, or both

A2. CLARIFICATIONS FOR EXCLUSION CRITERIA

Some exclusion criteria are represented by congenital disorders: when a patient is affected by these disorders his biology and physiology are significantly changed and are not eligible for the study and will not be randomized. If the condition has been discovered/suspected after the randomization but before the study inclusion (that is, before extubation), they will not receive the study intervention and will not entry in the study. If one of these conditions is diagnosed after the inclusion in the study, the neonate will be excluded *a posteriori*. This is the case of neonates with major congenital anomalies, chromosomal abnormalities, neuromuscular diseases, congenital upper respiratory tract abnormalities and congenital lung diseases or malformations or hypoplasia. Examples of these conditions are: genetic syndromes, surfactant protein defects, congenital adenomatous pulmonary malformations, congenital diaphragmatic hernia or sequestration, congenital hypoventilation syndrome, pulmonary hypoplasia or any metabolic disease.

A3. LIST OF STUDY DEFINITION

- **Gestational age (GA).** GA is determined based on sure dates of last menstrual period or early ultrasound scan (within the first trimester). If a discrepancy of more than 2 weeks exists, the early ultrasound scan will be chosen.
- **INSURE.** Intubation-Surfactant-Extubation
- **Antenatal steroids.** Antenatal steroid prophylaxis will be considered complete if two 12 mg doses of betamethasone 24h apart and between 1 day and 7 days before the delivery had been given.
- **Clinical Risk Index for Babies (CRIB-II) score.**⁴² This is an estimator of the clinical severity at the NICU admission. CRIB-II score considers 4 variables: *birth weight, GA, base excess within the 1st hour of life and temperature at*

theadmission(see below). An online calculator is available at

www.sfar.org/scores2/crib22.php

Birthweight (g) and gestation (weeks):

The maximum (worst) score for birthweight and gestation is 15, which is obtained for a 22 week male infant of less than 501 g birthweight

Male infants																Female infants																
Birthweight (g)	2751 to 3000																															0
	2501 to 2750																															1
	2251 to 2500																															3
	2001 to 2250																															2
	1751 to 2000																															3
	1501 to 1750																															6
	1251 to 1500																															5
	1001 to 1250																															3
	751 to 1000	12	10	9	8	8	7	6	5	4	3	3	2	1	0	0	11	10	8	7	6	5	4	3	3	3	3	2	1	1		
	501 to 750	14	13	12	11	10	9	8	8	8	8	8	6	6	6	13	12	11	10	9	8	7	6	5	5	5	5	5	5			
251 to 500	15	14	13	12	11	10	10								14	13	12	11	10	10												
Gestation (weeks)																Gestation (weeks)																

Temperature at admission (°C)

≤29.6	5
29.7 to 31.2	4
31.3 to 32.8	3
32.9 to 34.4	2
34.5 to 36	1
36.1 to 37.5	0
37.6 to 39.1	1
39.2 to 40.7	2
≥40.8	3

Base excess (mmol/L):

<-26	7
-26 to -23	6
-22 to -18	5
-17 to -13	4
-12 to -8	3
-7 to -3	2
-2 to 2	1
≥3	0

Sex, birthweight (g) and gestation (weeks):	_____
Temperature at admission (°C):	_____
Base excess (mmol/L):	_____
Total CRIB II Score	_____

The logistic regression equation relating CRIB II to mortality (CRIB II algorithm) is:
 Log odds of mortality = $G + 6.47 + 0.450 \times \text{CRIB II}$
 Probability of mortality = $\exp(G) / (1 + \exp(G))$
 The range of possible CRIB II scores is 0 to 27

Clinical risk index for babies II (CRIB II) score

- **Premature rupture of the membrane.** Premature rupture of the membrane will be considered complete if more than 18 hours.
- **Abdominal distension.** Abdominal circumference (cm) at 48h and 96h after study intervention.

References

3. Cumming JJ, Polin RA, AAP the COMMITTEE ON FETUS AND NEWBORN. Noninvasive respiratory support. Pediatrics2016; 137(1):

e20153758. <http://dx.doi.org/doi: 10.1542/peds.2015-3758>.

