(1) Resuscitation requiring early intubation according to the American Academy of Pediatrics guidelines for neonatal resuscitation [8]; (2)major congenital malformations or known complex congenital heart disease; (3)pulmonary hemorrhage or pneumothorax; (4) congenital lung diseases or malformations or pulmonary hypoplasia;

Setting

We plan to enroll preterm infants born between 26 and 34 weeks of gestational age from 18 tertiary NICUs in China. These 18 tertiary NICUs have more than 800 NICU beds and annual admissions of nearly 8,000 preterm infants with RDS each year. The first (XZ) and last authors (RR) take responsibility for the accuracy and completeness

of the trial.

Randomization

To avoid the chance of having more infants in one group than another, block randomization will be applied, with a block size of 4. The envelopes are sealed, shuffled, and then numbered in sequential order from 1 to 4. A clinician who is not in the trial group will open the envelope and randomize patients. This procedure will be repeated for each group of four infants. Infants will be stratified according to 26^{0/7}-27^{6/7} weeks, 28^{0/7}-29^{6/7} weeks, 30^{0/7}-31^{6/7} weeks and 32^{0/7}-33^{6/7} weeks. Infants born from multiple gestations will be assigned by individual randomization. Infants randomized to one arm cannot crossover to the other or vice-versa during the study.

Trial intervention

Ventilators

CPAP: CPAP will be provided by continuous flow devices (CNO Medin, Germany or Carefusion, USA) Bubble CPAP devices will not be used.

NHFOV: NHFOV will be provided by two ventilators (CNO, Medin, Germany or SLE 5000, UK). The Medin CNC ventilator produces high-frequency oscillations by flow interruption with cyclic opening-closure of the end expiratory valve. Otherwise, The SLE 5000 ventilator is a time-cycled, pressure-limited and continuous-flow neonatal ventilator.

Before the beginning of the study all ventilators will be checked to ensure that there is no malfunction.

Interfaces

CPAP and NHFOV will be all administered through short, low-resistance binasal prongs,

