since these are supposed to be the best in terms of resistive charge, leaks and/of comfort. Nasal prongs size will be chosen according to the nares' diameter as the best fitting ones (the largest ones that fit the nares without blanching the surrounding tissues) and following manufacturer's recommendations. Particular care (e.g.: pacifiers, positioning, nursing) will be applied to reduce leaks and improve patients' comfort. These matters will be evaluated through a dedicated 30 min observation period when study intervention will be instigated.

Ventilatory management

The two different respiratory supports will be managed as follows:

CPAP: Neonates assigned to the CPAP group were initiated on a pressure of 5 cmH₂O. CPAP can be raised in steps of 1 cmH₂O up to 10 cmH₂O. If this is not enough to maintain target oxygen saturation (SpO₂) from 89% to 92% in preterm infants <30 weeks GA and 90-94% in infants ≥30 weeks GA by pulse oximeter, FiO₂ will be added up to 0.40.

NHFOV: For Medin CNO, the initial NHFOV settings will be: mean airway pressure (MAP) of 6cmH₂O (range 6-10cmH₂O), frequency of 10 Hz (range 6-12), The Medin CNO has ten grades of amplitude. grade 7th amplitude will be to start with (grade range 7th-10th). For SLE 5000, The initial settings will be: MAP of 6 cm H₂O (range 6-10cmH₂O); frequency of 10Hz (range 6-12), inspiratory time 50% (1:1), oscillations of amplitude of 20 cm H₂O (range 20-35 cm H₂O). It is not strictly necessary to have visible chest oscillations, as most of the CO₂ elimination during NHFOV will occur in the upper airway dead space. Maximal allowed FiO₂ will be 0.40 and SpO₂ from 89% to 93% in

preterm infants <30 weeks GA and 90-94% in infants \geq 30 weeks GA by pulse oximeter.

Surfactant Therapy

Surfactant (Poractant alfa, Chiesi Pharmaceuticals, Parma, Italy) at dose of 200 mg/kg will be administered via INSURE method if infant presents with the following: infants \leq 26 week's gestation when FiO_2 requirement >0.30 and infants >26 week's gestation when FiO_2 requirement >0.40 [2]. Additional doses of surfactant may be given using INSURE technique at the discretion of the clinician.

Caffeine Therapy

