The primary outcome of this trial will be to determine the need for IMV in the first 7 days of life in preterm infants randomized to the two groups. Secondary outcomes include days of hospitalization, days on noninvasive ventilation, days on supplemental oxygen, pre-discharge mortality, surfactant doses, incidence of stage III ROP and BPD, occurrences of abdominal distention, air leaks, IVH \geq grade 3 and NEC. Secondary outcomes also include Bayley Scales of Infant Development at 18-24 months of corrected age. BPD will be defined according to the National Institutes of Health consensus definition as mild, moderate and severe BPD [12], IVH classification according to Papile et al [13] and for NEC, Bell staging will be used [14].

Data collection

Patient demographic data include: sex, birth weight, gestational age, Apgar scores, mode of

delivery, prenatal corticosteroid use, premature rupture of the membrane, RDS Silverman score and critical risk index for babies-II (CRIB-II) score. More details see in the appendix Clinical data :Including the need for IMV, days of hospitalization, days on noninvasive respiratory support, days on supplemental oxygen, mortality, the need for surfactant, occurrences of abdominal distention, air leaks, IVH \geq grade and NEC \geq stage II. More details see in the appendix Follow-up data: The incidence of BPD and ROP at a post-menstrual age of 36 weeks or at discharge, and Bayley Scales of Infant Development at 18-24 months of corrected age.

Sample size calculation

It is difficult to calculate a sample size for such a study, since it is the first to investigate NHFOV vs CPAP in primary support phase in preterm infants with RDS. There is only one preliminary study available about the primary outcome “need for IMV”. This pilot study conducted by Zhu et al provides data about the primary outcome “need for IMV”. This trial showed the need for IMV was significantly lower in the NHFOV compared with the NCPAP group (24.3% vs. 56.4%, $P < 0.01$). Considering an α -error of 0.05 and a power of 90%, 150 neonates should be enrolled in each arm (with a 1:1 design) to detect the same difference.

Statistical methods

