Data will be analyzed using SPSS version 19 software. The statistical analyses include Student's t-test for continuous data and compared proportions using Chi-squared test, and Fisher's exact test for categorical data. Predefined four subgroups are 26^{0/7}-27^{6/7} weeks, 28^{0/7}-29^{6/7} weeks, 30^{0/7}-31^{6/7} weeks and 32^{0/7}-33^{6/7} weeks, and subgroup analyses will be conducted for the primary outcome in the preterm infants. To further evaluate the effect of NHFOV on intubation within

subgroup, the test of treatment-by-gestational age subgroup interaction will also be done using the paired binary logistic regression. For the preterm infants lost to follow-up, the missing values of the primary and secondary outcomes are replaced using multiple imputation. A P -value < 0.05 will be regarded as statistically significant.

Data Safety Monitoring Board (DSMB): [name], Professor of Pediatrics, Oklahoma University Medical Center, Oklahoma, [name], Professor of Pediatrics, Medical College of Georgia, Georgia Health Sciences University, Augusta, Georgia, and [name], MD., MPH (Biostatistics and Epidemiology) Assistant Professor of Pediatrics, Keck School of Medicine of the University of Southern California, Los Angeles, California will serve as DSMB members. [name] will also serve as consultant for statistical analysis.

Registration number

The trial has been approved by the centralized ethics committee (The Ethics Committee of Daping Hospital, Research Institute of Surgery, Third Military Medical University) and registered at <http://www.clinicaltrials.gov>(ID: NCT03099694).

Discussion

In the past decades, several clinical trials have compared the effects between NHFOV and NCPAP in neonates as a rescue mode or during weaning from IMV. These trials demonstrated that NHFOV applied with nasopharyngeal tube are more beneficial than NCPAP in reducing CO₂ levels [16-19]. Recently, two retrospective case series also reported NHFOV could be applied in preterm infants as a rescue treatment after the

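### Appendix A2 drops randomised infants after allocation, with no time limit or blinded adjudication, and no all-randomised analysis is specified

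*Combined protocol and SAP*

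**What the plan says.** Appendix A2 (Clarifications for exclusion criteria) has two rules that act after randomisation.

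- Before study inclusion, for infants whose condition is found or merely suspected once they have been randomised: "before the study inclusion (that is, before extubation), they will not receive the study intervention and will not entry in the study". Suspicion is enough.
- After study inclusion: "If one of these conditions is diagnosed after the inclusion in the study, the neonate will be excluded". The removal is retrospective, and no latest date is given.

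The conditions in A2 are wider than those in Exclusion criteria. The main list has "major congenital malformations or known complex congenital heart disease" and congenital lung disease, malformation or hypoplasia. A2 adds "chromosomal abnormalities, neuromuscular diseases, congenital upper respiratory tract abnormalities", and its examples extend to congenital hypoventilation and any metabolic disease.

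Outcomes describes the primary outcome as the "need for IMV in the first 7 days of life in preterm infants randomized to the two groups". Statistical methods lists tests, subgroups and imputation, but no intention-to-treat, all-randomised or per-protocol set. Its only rule for absent data is: "For the preterm infants lost to follow-up, the missing values of the primary and secondary outcomes are replaced using multiple imputation".

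**The concern.** Randomisation protects the comparison only if the infants analysed are those randomised, or if any removal is unrelated to arm and outcome. A2 secures neither. The primary outcome is settled within the first week, while follow-up runs to 18-24 months corrected age, so the text allows an infant to be removed once the result is known. No blinding of clinicians or assessors is described; the envelope procedure concerns allocation only.

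The allocated mode cannot cause a congenital condition, but it can affect who is investigated for one. Surfactant protein defects, pulmonary hypoplasia and hypoventilation are plausibly looked for most in infants who do badly on support. Appendix A1 adds to this: it defines RDS partly by a good response to surfactant or recruitment, so a poor response itself calls the diagnosis into question. Exclusion can therefore depend on the primary outcome. If detection or the decision to exclude also differs by arm, the estimated effect is biased, and which mode benefits depends on which arm loses more failures.

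**Working it through.** **Does another section repair the rule?** No. The imputation rule covers infants lost to follow-up, and an infant excluded by A2 is not lost. The ban on crossover in Randomization concerns treatment and does not define an analysis set. The reference to randomised infants in Outcomes describes the comparison but does not say that A2 exclusions are put back.

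**Is the boundary between the two rules usable?** A2 equates study inclusion with extubation. This trial tests primary support and excludes infants who need early intubation at resuscitation, so many infants will have no extubation. Surfactant "will be administered via INSURE method if infant presents with the following" criteria are met, so for infants treated this way extubation may come after study support has begun. The point at which one rule gives way to the other is undefined.

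**How large could the effect be?** The plan gives no exclusion frequency, so there is no figure of its own to reproduce and every exclusion count below is an assumption. The inputs from Sample size calculation are 150 infants per arm and pilot IMV rates of 24.3% (NHFOV) and 56.4% (NCPAP).

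*Fixed tables near the threshold.* The starting point of 55/150 versus 70/150 was chosen to be borderline. A removed failure leaves both numerator and denominator. Two-sided p-values:

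| Failures removed | NHFOV | NCPAP | Chi-squared | Continuity-corrected | Fisher |
|---|---|---|---|---|---|
| None | 55/150 | 70/150 | 0.079 | 0.101 | 0.101 |
| 3 NHFOV | 52/147 | 70/150 | 0.048 | 0.063 | 0.059 |
| 5 NHFOV | 50/145 | 70/150 | 0.033 | 0.044 | 0.044 |
| 3 NHFOV, 4 NCPAP | 52/147 | 66/146 | 0.086 | 0.110 | 0.096 |
| 3 NCPAP | 55/150 | 67/147 | 0.119 | 0.149 | 0.127 |
| 5 NCPAP | 55/150 | 65/145 | 0.154 | 0.191 | 0.158 |

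Roughly proportional removal leaves the result about where it was. One-sided removal moves it either way.

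*No true effect.* Take a common IMV rate p = (24.3% + 56.4%)/2 = 40.4%. If a share r of failures is removed from an arm, its expected rate becomes p(1 - r)/(1 - pr).

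- r = 5%: 0.404 × 0.95/(1 - 0.0202) = 0.3838/0.9798 = 39.2%, a shift of -1.2 points.
- r = 10%: 0.404 × 0.90/(1 - 0.0404) = 0.3636/0.9596 = 37.9%, a shift of -2.5 points.

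Simulating 400,000 trials per setting with 150 per arm and the uncorrected test gives:

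| Share of failures removed (NHFOV / NCPAP) | Shift in difference | Two-sided type I error |
|---|---|---|
| 0 / 0 | 0.0 points | 5.2% |
| 5% / 5% | 0.0 points | 5.0% |
| 5% / 0 | -1.2 points | 5.6% |
| 10% / 5% | -1.3 points | 5.6% |
| 10% / 0 | -2.5 points | 7.3% |
| 0 / 5% | +1.2 points | 5.6% |

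Rejections favouring NHFOV rise from 2.6% with no exclusions to 4.1% in the 5% / 0 case. For common rates from 24% to 56.4%, the 5% / 0 shift is -0.9 to -1.3 points and the 10% / 0 shift is -1.9 to -2.6 points.

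*Pilot-sized effect.* The pilot rates give about 36/150 versus 85/150. Removing 5 NHFOV failures (31/145 versus 85/150) or 20 NCPAP failures (36/150 versus 65/130) leaves p<0.0001.

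**The case against.** The strongest reply is that these infants were never eligible. The conditions predate allocation, the main criteria already exclude several of them at entry, and A2 reaches only those missed at under 12 hours of age. They may be few. Bias then needs a chain that the documents do not evidence: failing infants are investigated more, a listed condition is found, and detection or exclusion differs by arm. The borderline table was chosen to be borderline, and removing three infants crosses 0.05 only on the uncorrected test. Against the 5.2% baseline, one-sided removal of 5% of failures adds only about 0.4 points of type I error. Removal as late as 18-24 months is inferred from the absence of a limit and is not a stated plan. Finally, excluding objectively confirmed, pre-existing ineligibility can be defended if it is judged blind and within a fixed window.

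Much of this stands as a limit on size: the effect is probably small, and its likelihood cannot be read from the documents. It does not answer the point about the rule. The defence of excluding ineligible infants depends on blinded, time-limited judgement, and A2 provides neither. It also acts on suspicion alone and uses an open-ended list.

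**Conclusion.** The concern holds and should be fixed. The textual facts are certain: A2 removes infants after randomisation by two routes, without a time limit or blinded adjudication, and no all-randomised analysis is specified. The bias is conditional. It needs exclusion related to the outcome and at different rates by arm; equal removal of failures produces none. Under assumed one-sided removal of 5% to 10% of failures and a 40.4% IMV rate, the difference shifts by 1.2 to 2.5 points and type I error rises from 5.2% to between 5.6% and 7.3%. That could decide a borderline trial. It would not overturn a difference as large as the pilot's, but the protocol says that only one preliminary study is available, so a smaller true effect is possible.

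**What to change.** Add to Statistical methods: *The primary analysis includes all randomised infants in the arm assigned, whatever is diagnosed later.* In Appendix A2:

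- Make randomisation the point of study entry for analysis, in place of extubation.
- Confine the removal of late-diagnosed infants to a sensitivity analysis, limited to the conditions in Exclusion criteria and judged by assessors blind to arm and outcome, within a stated window.
- Report these infants by arm, with the reason and time of diagnosis.
- Reconcile the A2 list of conditions with Exclusion criteria.

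If the sponsor prefers to keep an exclusion in the primary analysis, blinded and time-limited adjudication of pre-existing conditions is the minimum. Analysing everyone as assigned is simpler and needs no such judgement.

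The cost is protocol and appendix wording, and outcome data kept for every randomised infant. The sample size does not change. A few infants with congenital disease stay in the primary analysis and may slightly dilute the effect. The change concerns the analysis set only, not the care any infant receives.

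### Appendix A2 adds exclusions that the main list lacks and sets study inclusion at extubation, which does not fit a trial of primary support and leaves room for avoidable removals after randomisation

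*Combined protocol and SAP*

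**What the plan says.** The Exclusion criteria section has four items: "Resuscitation requiring early intubation" under resuscitation guidelines; "major congenital malformations or known complex congenital heart disease"; pulmonary haemorrhage or pneumothorax; and "congenital lung diseases or malformations or pulmonary hypoplasia".

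Appendix A2 (Clarifications for exclusion criteria) gives a second list. Besides major congenital anomalies it names "chromosomal abnormalities, neuromuscular diseases, congenital upper respiratory tract abnormalities and congenital lung diseases". Its examples end with "congenital hypoventilation syndrome, pulmonary hypoplasia or any metabolic disease".

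A2 then sets three rules:

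- **Before randomisation:** affected infants "are not eligible for the study and will not be randomized".
- **Between randomisation and inclusion:** if the condition is "discovered/suspected after the randomization but before the study inclusion (that is, before extubation), they will not receive the study intervention" and do not enter the study.
- **After inclusion:** an infant in whom such a condition is diagnosed is excluded a posteriori, with no time limit.

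The Statistical methods section names no analysis population. Its multiple imputation covers infants lost to follow-up and does not mention infants removed under A2.

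**The concern.** There are two faults, and both act on who is counted.

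First, a clarification should explain the criteria, not add to them. With 18 centres, those screening from the main section and those screening from the appendix could admit different infants. Where an added disorder was already evident, randomising the infant and removing it afterwards would have been avoidable.

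Second, the inclusion point belongs to a design in which study support starts at extubation. Here support starts as the primary mode before 12 hours of age. An entry point that many infants never reach cannot be applied consistently. It also matters which side of it an infant is on, because suspicion is enough for removal before it and a diagnosis is required after it.

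At stake is the comparability of the randomised arms. Staff can see which support an infant receives, and no blinded review of removals is described. If infants who do badly are investigated more, removals could differ between arms and be related to outcome.

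**Working it through.** **1. The two lists side by side**

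| Category in A2 | In the Exclusion criteria section? |
|---|---|
| Major congenital anomalies | Yes, as major malformations |
| Congenital lung disease, malformation, hypoplasia | Yes |
| Chromosomal abnormalities | Not named |
| Neuromuscular diseases | Not named |
| Congenital upper respiratory tract abnormalities | Not named (some may count as major malformations) |
| Any metabolic disease (an example) | Not named |

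A neuromuscular or metabolic disease is not a malformation in the ordinary sense, so A2 adds content.

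**2. Where extubation can occur**

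- Inclusion criteria: age under 12 hours, with noninvasive support as the primary mode.
- Exclusion criteria: infants intubated early at resuscitation do not enter.
- Surfactant Therapy and Appendix A3: INSURE comprises intubation, surfactant and extubation.
- Criteria for intubation and IMV: IMV is the other route to a tube.

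So the plan provides for no extubation before study support. An infant with neither INSURE nor IMV has no extubation and, read literally, is never included. An infant on IMV is not yet included although the primary outcome has already occurred.

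**3. Size**

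The plan gives no figure on this point, so there is none to reproduce. It gives neither the frequency of these disorders nor a count of expected removals. The following is therefore a worst-case illustration.

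Inputs:

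- 150 per arm (Sample size calculation).
- IMV rate 40%, assumed. It is close to the midpoint of the planning rates: (24.3 + 56.4)/2 = 40.35%.
- k = 3 or 5 removals, assumed, all from one arm and all IMV cases.

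Rate in that arm after removal = (60 − k)/(150 − k):

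- k = 0: 60/150 = 40.0%
- k = 3: 57/147 = 38.8%
- k = 5: 55/145 = 37.9%

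The spurious difference is 1.2 or 2.1 percentage points.

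With no true effect, the type I error (two-sided 5% test assumed, normal approximation) follows from a shift δ = d/√[p(1−p)(1/150 + 1/(150−k))], where d is the spurious difference. The error is 1 − Φ(1.96 − δ) + Φ(−1.96 − δ). For p = 0.40 and k = 3, δ = 0.0122/0.0569 = 0.215 and the error is 5.5%.

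| IMV rate in both arms | k = 3: difference, error | k = 5: difference, error |
|---|---|---|
| 24.3% | 1.5 points, 6.1% | 2.6 points, 8.2% |
| 40.0% | 1.2 points, 5.5% | 2.1 points, 6.5% |
| 56.4% | 0.9 points, 5.3% | 1.5 points, 5.8% |

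Lost numbers are not the issue. At the planning rates of 24.3% and 56.4%, removing up to 15 infants from each arm leaves power above 99.9%.

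**The case against.** A2 is part of the same protocol and says that affected infants will not be randomised. A reader might infer that the plan permits randomising an infant with a known disorder and then removing it. **It does not.** A2's removal rules cover conditions discovered, suspected or diagnosed after randomisation. A known disorder gets through only if a site works from the main section alone. That is a risk created by two unreconciled lists, not a permission.

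A reader might also infer that removal is tied to the primary outcome. **The documents do not establish that.**

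- A2 removes affected infants on both sides of the inclusion point. The point changes only whether suspicion is enough.
- A never-intubated infant also stays on the looser side, so removal is not reserved for intubated infants.
- Extubation may follow INSURE, which the documents do not show to count as IMV.
- The earlier clause speaks of infants who will not receive the intervention, which sits badly with an infant already on study support.
- The Abstract counts the outcome from enrolment, but nothing equates enrolment with A2's inclusion, so a clock starting at extubation would be a further inference.

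The lists also overlap: A2's lung malformations and hypoplasia fall under the main criteria. The documents do not say which added disorders would be recognisable by 12 hours of age. The illustration rests on assumed one-sided removals and is small beside the planned difference of 56.4 − 24.3 = 32.1 points.

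All of this stands. It limits the point but leaves the added categories, an inclusion event that does not fit the design, and removal after randomisation without described safeguards.

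**Conclusion.** The point holds in limited form. A2 adds four kinds of disorder that the main list does not name, and it defines inclusion by an event that, in this design, happens only after allocation and only in some infants. On a literal reading, a randomised infant can be dropped on suspicion until extubated, and a never-intubated infant never enters. This is a stated rule that cannot be followed as written, not merely a missing detail.

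The size of any bias cannot be derived from the documents. The shift of 1.2 to 2.1 points at a 40% rate, and a type I error of 5.3% to 8.2% across the three rates tried, require every removal to be an IMV case from the same arm. Removals unrelated to arm and outcome would not produce this bias. The point is worth correcting because the correction is cheap, not because a large distortion has been shown.

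**What to change.** 1. **Reconcile the two lists** into one, placed in the Exclusion criteria section and applied before randomisation to what is known then. Which disorders belong on it is a clinical decision for the sponsor.
2. **Define study entry as randomisation.** Delete the A2 clause on conditions discovered or suspected between randomisation and extubation. Merely substituting randomisation for inclusion within that clause would leave an empty window.
3. **Keep infants diagnosed after randomisation in the primary analysis**, and use A2's a posteriori exclusion only in a sensitivity analysis. Without this step the open-ended removal would remain. State the population in Statistical methods.

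This concerns who is analysed. It takes no position on the respiratory support that an infant with a late-found disorder should receive.

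The cost is a wording amendment, one updated screening form, and a few infants with late-found disorders in the primary analysis, where they may slightly dilute the effect.
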